The doses will be escalated until participants are on their full dose by 1 month. If a patient encounters intolerable side effects at full dose, then they will be able to remain on the highest dose regime that they can tolerate and this dose will be recorded. The total duration of the trial drug administration will be 1 year.

Note that no maximum time since the index lacunar ischaemic stroke will be set – patients will be eligible for the trial for several years after their lacunar stroke at the discretion of the local medical staff, as long as the index stroke was compatible with lacunar ischaemic stroke and competing pathologies as a cause of the stroke were excluded using contemporaneous MR imaging, or CT, as above. That is, that the index stroke was not a non-lacunar stroke, that it was ischaemic and not haemorrhagic, and that it was not a non-stroke based on clinical and MR imaging, or CT, acquired at the time of the stroke.

Note also that no minimum cut off cognitive score is set. The Montreal Cognitive Assessment (MOCA) will be collected at baseline but will not be an inclusion/exclusion criterion. The important point is that the patient has capacity to consent, in the opinion of the randomising doctor.

[figure not shown]
Throughout the trial, patients will continue to take their normal prescribed medication which will include stroke secondary prevention prescribed since their event as per national guidelines/usual post-stroke care in participating centres.

Four hundred patients will be recruited from UK stroke research network centres. The most active of these sites see 10-15 patients per month with suspected lacunar stroke, of whom 25-33% would be eligible. Some interested sites have indicated that they could randomise 1-2 per month. Patients will be recruited from hospital-based stroke services, including patients who have participated in previous completed studies and indicated that they would like to be informed of future stroke studies.

On entry to the study, participants will be assessed by the study researcher, including presenting history, past medical history, medication history, neurological examination, check of brain MR or CT scan, blood pressure measurement and cognitive testing. They will then be randomised.

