Haematology (full blood count) and Biochemistry (urea, electrolytes, creatinine) – most recent value obtained since time of index stroke is acceptable unless clinical reason to expect change		X ^s				
Blood pressure		X ^s				X ^s [‡]
Cognitive test: document years of education; Montreal Cognitive Assessment (MOCA)		X ^s				
Timed Trail Making Test B		X ^s				X ^s [‡]
Dispense trial medication ²		X ^s			X ^s	
Structured questionnaire: symptoms; medication history and IMP tablet adherence			X ^s	X ^s	X ^c	X ^c
Structured questionnaire: recurrent vascular events, mRS, TICS, t-MOCA, SIS, ZUNG					X ^c	X ^c
Obtain IQCODE (post/phone) from relative						X ^c
Follow-up brain MRI						X ^s
Health Economics data: EQ-5D-5L, EQ-VAS						X ^c
Adverse event / con meds reporting as necessary			X ^s	X ^s	X ^{s,c}	X ^{s,c}

[†] Consent will be obtained before the data collection procedures commence or randomisation is performed. Randomisation occurs at the end of the baseline visit.

[‡] at 12 months in some centres only.

² Dispensing in 3-monthly intervals is allowed.

^s Assessment performed by local site team.

^c Assessment performed by blinded assessor who is part of the central trial team.

SIS: Stroke Impact Scale; TICS: telephone interview for cognitive status; t-MOCA: telephone MOCA.

SECTION 4. STATISTICAL PRINCIPLES

Confidence and p values**16 Level of statistical significance**

The results of analyses and comparisons will be shown with $p < 0.05$.

17 Multiplicity

No adjustment will be made for multiplicity.

18 Levels of confidence intervals

The results of analyses and comparisons will be shown with 95% confidence intervals.

19 Adherence

19a Definition: 75% of patients will be able to tolerate trial medication, in at least half dose, up to one year after randomisation (i.e. less than 25% will stop trial medication completely through inability to tolerate the drugs).

19b Adherence presentation: See Table 4.

19c Protocol deviations: Protocol violations will be reported to the sponsor within 24 hours of becoming aware of the violation. Protocol deviations will be recorded in a protocol deviation log with these submitted to the sponsors every 3 months.

19d Protocol deviation presentation: Listing of violations and deviations and their frequency.

20 Analysis populations

Three populations are defined:

1. Intention-to-treat: All consented participants with a primary outcome measure.

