2. Per protocol: All consented participants with a primary outcome measure who received at least one dose of randomised medication and who had no protocol violation, e.g. they fulfilled all eligibility criteria.
3. Safety: All consented participants who received at least one dose of randomised medication.

Multiple variable analyses will include all patients with complete data for the dependent and each independent variable. All available data will be used, and missing data will not be imputed.

SECTION 5. TRIAL POPULATION**21 Screening data**

No screening logs will be kept so that data collection can be prioritised.

22 Eligibility

1. Clinical lacunar stroke syndrome.
2. Brain scanning with MR including diffusion imaging wherever possible, and obtained soon after the presentation with stroke, which showed either:
 - a. A recent, relevant (in time and location) acute small subcortical (i.e. lacunar) infarct on diffusion MR imaging.
 - b. If no visible acute small subcortical infarct on diffusion MR imaging then there is no competing pathology as a cause for stroke (e.g. no acute cortical infarct, no acute intra-cerebral haemorrhage, no stroke mimic such as tumour, subdural haematoma);
 - c. If only a CT brain scan is available, then there is a small relevant (in time and location) subcortical (i.e. acute lacunar) infarct, or if no infarct then there is no competing pathology as a cause for stroke (e.g. no acute cortical infarct, no acute intra-cerebral haemorrhage, no stroke mimic such as tumour, subdural haematoma).

3. Age >30 years.
4. Independent in activities of daily living (modified Rankin Scale <=2).
5. Capacity to give consent themselves.

23 Recruitment

Recruitment will be summarised in a CONSORT flow diagram.

24 Withdrawal/follow-up

Withdrawals, and missed follow-ups and their timing will be summarised in the CONSORT flow diagram.

25 Baseline patient characteristics

25a Baseline characteristics: These will comprise demographic, education, premorbid function, cognitive ability, medical history, blood pressure, stroke investigations, clinical and brain imaging parameters (Table 1).

25b Summarisation: Data will be shown as number (%), median [interquartile range] or mean (standard deviation) as appropriate.

SECTION 6. ANALYSIS

26 Outcome definitions

26a Specifications:

Primary endpoint

Feasibility of a Phase III efficacy trial assessed as:

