27e Sensitivity analyses: In addition to assessment of raw data, the primary outcome will be analysed using additional statistical approaches in sensitivity analyses:

- Unadjusted analysis
- Imputation (multiple regression imputation) of missing data (adjusted)¹⁶

27f Subgroup analyses: The secondary endpoint of the composite of: recurrent stroke, MI, death, cognitive impairment and dependency, will be studied in:

- Pre-specified subgroups comprising the minimisation variables.
- Any other variables demonstrating imbalance at baseline.

The results of these subgroup analyses will not be adjusted for multiple testing. These analyses are planned for the phase III efficacy trial and so will be tested in the present study.

28 Missing data

Missing data may occur at outcome level or at test level or within a test at component item level. Notably, some tests have to exclude components if performed by telephone and/or postal questionnaire or require a one year MRI. There is often a relationship between inability to complete outcome assessment and cognitive function or neurological deficit after stroke (e.g. inability to hold a pen) and so assumptions around random missingness may not be valid, even if the patterns of missing data initially suggest 'missing completely at random' status. Indeed, failure to complete a test may be an indicator of cognitive impairment rather than real missingness.

The approaches taken to missing cognitive and other data can have a substantial effect on epidemiological estimates.¹⁶ We will use the approach that makes greatest use of available data.

Where in study data are not available, or participants are lost to follow-up, we have permissions to allow for linkage of the study dataset to primary and secondary care electronic health records. This will allow for an assessment of clinical outcomes across all the participants.

29 Additional analyses

Global outcomes

We will assess global outcomes integrating multiple scores into one analysis and so provide a more holistic measure and improve statistical power. We will assess global outcomes comprising:

- Recurrent ordinal stroke (clinically-evident and/or imaging-detected),¹⁷ ordinal MI, cognition (MoCA), dependency (mRS), quality of life (EQ-5D).

Analyses will use the Wei-Lachin test¹⁸⁻²¹ with comparison of data at 1 year.

Cognitive domains, based on DSM-V

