Heart rate (bpm)	XX (X)	XX (X)	MLR	XX (X)	XX (X)	MLR	XX (X)	XX (X)	MLR
mRS	XX (X)	XX (X)	OLR	XX (X)	XX (X)	OLR	XX (X)	XX (X)	OLR
Disposition	XX (X)	XX (X)	OLR	XX (X)	XX (X)	OLR	XX (X)	XX (X)	OLR
ZDS	XX (X)	XX (X)	MLR	XX (X)	XX (X)	MLR	XX (X)	XX (X)	MLR
Clinical depression	XX (X)	XX (X)	BLR	XX (X)	XX (X)	BLR	XX (X)	XX (X)	BLR
EQ-5D-5L, as HU	XX (X)	XX (X)	MLR	XX (X)	XX (X)	MLR	XX (X)	XX (X)	MLR
EQ-VAS	XX (X)	XX (X)	MLR	XX (X)	XX (X)	MLR	XX (X)	XX (X)	MLR
SIS	XX (X)	XX (X)	MLR	XX (X)	XX (X)	MLR	XX (X)	XX (X)	MLR
Global	XX (X)	XX (X)	WLT	XX (X)	XX (X)	WLT	XX (X)	XX (X)	WLT

BP: blood pressure; MoCA: Montreal cognitive assessment-modified; mRS: modified Rankin Scale; SIS: stroke impact scale; TICS-m: Telephone interview cognitive status- modified; ZDS: Zung depression scale
 Global: Recurrent ordinal stroke,¹⁷ ordinal MI, cognition (MoCA), dependency (mRS), stroke impact scale, quality of life (EQ-5D).

Table 4. Adherence to medication with at least half dose or more by randomised group: isosorbide mononitrate (ISMN), cilostazol (Cil) and both together.

Week	ISMN	No ISMN	p	Cilostazol	No cilostazol	p	ISMN +Cil	ISMN alone	Cil only	Neither	p
1-2	XX (X)	XX (X)	Chi-sq	XX (X)	XX (X)	Chi-sq	XX (X)	XX (X)	XX (X)	XX (X)	Chi-sq
3-4	XX (X)	XX (X)	Chi-sq	XX (X)	XX (X)	Chi-sq	XX (X)	XX (X)	XX (X)	XX (X)	Chi-sq
26	XX (X)	XX (X)	Chi-sq	XX (X)	XX (X)	Chi-sq	XX (X)	XX (X)	XX (X)	XX (X)	Chi-sq
52	XX (X)	XX (X)	Chi-sq	XX (X)	XX (X)	Chi-sq	XX (X)	XX (X)	XX (X)	XX (X)	Chi-sq

A more detailed table by strata of drug adherence (i.e. 25%, 50%, 75% and 100% adherence) will also be prepared.

Table 5. Adjudicated baseline imaging characteristics by randomised group: isosorbide mononitrate (ISMN), cilostazol (Cil) and both together.

Data are number (%), median [IQR], or mean (standard deviation).

	N	All	ISMN	No ISMN	Cil	No Cil	ISMN + Cil	ISMN only	Cil only	None
Patients randomised	XX	XX	XX	XX	XX	XX	XX	XX	XX	XX
Scan										
Scan type(%)										
CT	XX	XX (X)	XX (X)	XX (X)	XX (X)	XX (X)	XX (X)	XX (X)	XX (X)	XX (X)
Time to scan (days)	XX	XX (X)	XX (X)	XX (X)	XX (X)	XX (X)	XX (X)	XX (X)	XX (X)	XX (X)
MR	XX	XX (X)	XX (X)	XX (X)	XX (X)	XX (X)	XX (X)	XX (X)	XX (X)	XX (X)
Time to scan (days)	XX	XX (X)	XX (X)	XX (X)	XX (X)	XX (X)	XX (X)	XX (X)	XX (X)	XX (X)
Scan quality (%)										
Good	XX	XX (X)	XX (X)	XX (X)	XX (X)	XX (X)	XX (X)	XX (X)	XX (X)	XX (X)
Moderate	XX	XX (X)	XX (X)	XX (X)	XX (X)	XX (X)	XX (X)	XX (X)	XX (X)	XX (X)

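### The Wei-Lachin global outcome is defined in two different ways in the SAP, its 12-month cognitive test is not identified, and death has no score on several of its scales

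*SAP*

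**What the plan says.** **Components.** SAP section 29 (Global outcomes) opens its list with "Recurrent ordinal stroke (clinically-evident and/or imaging-detected") and continues "ordinal MI, cognition (MoCA), dependency (mRS), quality of life (EQ-5D"). The test is the Wei-Lachin test "with comparison of data at 1 year". The footnote to SAP Table 3, which explains the row labelled Global, starts with recurrent ordinal stroke, without the clinical/imaging qualifier, and continues "ordinal MI, cognition (MoCA), dependency (mRS), stroke impact scale, quality of life (EQ-5D").

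**Cognitive instrument.** In SAP Table C the row "Cognitive test: document years of education; Montreal Cognitive Assessment (MOCA") is marked at baseline only, and Protocol section 3 agrees: "The Montreal Cognitive Assessment (MOCA) will be collected at baseline". At 6 and 12 months the row is "Structured questionnaire: recurrent vascular events, mRS, TICS, t-MOCA, SIS, ZUNG". The Table 3 footnote expands MoCA as a modified MoCA. Section 26c derives the trail item of that modified score from Trails B, and Table C has Trails B repeated at 12 months in only some centres. Table E works with T-MoCA, normal range 20–22.

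**Death and missing values.** Table E codes death as mRS 6 and as the worst level of both the 7-level and the 4-level cognition scale. No score for death is given for MoCA, TICS-m, EQ-5D, EQ-VAS, SIS or ZDS. Section 20 states: "Multiple variable analyses will include all patients with complete data for the dependent and each independent variable", and adds that all available data are used and missing values are not imputed. Section 28 prefers whichever approach uses most of the available data. The imputation in section 27e is for the primary outcome only, which is recruitment and retention.

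**The concern.** The global outcome is presented as a more holistic and more powerful measure. It is reported in Table 3 for all three treatment comparisons and is one of three outcomes with subgroup forest plots (Figures 4a–c). Two definitions of one reported outcome cannot both be followed. With no adjustment for multiplicity, the choice between them could be made after results are seen. The opportunity is concrete, because section 13a has provisional data analysed at a soft lock before the final lock.

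The gap in scoring death matters for a different reason. A mean difference on EQ-5D or SIS calculated in survivors only does not register a treatment that increases mortality, and it compares groups that are no longer exactly as randomised. If the same happens inside the global test, a measure meant to summarise overall outcome gives too little weight to the worst one.

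**Working it through.** The documents give no power or effect size for this test, so there is no stated figure to reproduce. The check is a comparison of the text, followed by arithmetic on size and an illustrative simulation.

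**1. The two definitions side by side**

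| | SAP section 29 | Table 3 footnote |
|---|---|---|
| Stroke | ordinal, clinical and/or imaging-detected | ordinal, no qualifier |
| MI | ordinal | ordinal |
| Cognition | MoCA | MoCA (modified) |
| Dependency | mRS | mRS |
| Stroke Impact Scale | absent | included |
| Quality of life | EQ-5D | EQ-5D |
| Components | 5 | 6 |

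The precedence rule in SAP section 4c ranks the SAP above the protocol. It cannot settle a conflict inside the SAP, and Protocol section 9.2 names no global test. If components are weighted equally (an assumption; the SAP states no weights), cognition falls from 1/5 = 20% to 1/6 = 16.7%. Measures of function (mRS, plus the mobility and physical sections of the SIS) rise from 1/5 = 20% to 2/6 = 33.3%.

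**2. Number of deaths.** The inputs are 363 recruited (SAP Table 2), all-cause death 2.0% (section 11a), and vascular plus non-vascular death in Table A, 1.8% + 0.5% = 2.3%.

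- 363 × 0.020 = 7.3
- 363 × 0.023 = 8.3
- at the upper limit of 4% in section 11a, 363 × 0.04 = 14.5

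So 7–8 deaths are expected, about 4 in each half of a factorial comparison.

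**3. Where those deaths go**

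- Table 3 rows that carry death: mRS, 7-level cognition, 4-level cognition.
- Table 3 rows with no score for death, analysed by linear regression under section 20: MoCA, TICS-m, EQ-5D, EQ-VAS, SIS, ZDS.
- Global test: mRS carries death. MoCA and EQ-5D (2 of 5), plus SIS in the longer list (3 of 6), have no score for it. Whether the ordinal stroke and MI scales have a fatal level cannot be seen from the documents.

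**4. Partly missing components.** Protocol section 9.1 expects at least 15% to miss the repeat MRI: 363 × 0.15 = 54. If every component had to be complete and imaging-detected stroke were one of them, this would remove more patients than death.

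**5. Illustrative simulation.** A rank-based, equally weighted sum test was run with n = 363 randomised 1:1, 1,000 runs per scenario, correlation between components 0.4 or 0.7, and a true benefit of 0 or 0.2 SD on every component. These settings are assumptions. The few runs in which the statistic was undefined (0 to 3 per 1,000) do not affect the results.

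- Five versus six components: the p<0.05 verdict differed in about 3% of runs with no benefit and in 7–10% with a 0.2 SD benefit.
- Deaths ranked worst versus dropped, 2% dying in both arms: the verdict differed in 3–9% of runs.
- Deaths 4% on active treatment versus 2% on control, with a 0.2 SD benefit on the other measures: the five-component test was significant in 44% of runs with deaths ranked worst, 56% with deaths counted on mRS only, and 61% with deaths dropped.

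**The case against.** The strongest reply is that a reader might infer that patients who die are excluded from the global test, and the SAP does not say so. The complete-data sentence concerns multiple variable analyses and is followed by a commitment to use all available data. Section 28 points the same way, mRS is in both lists, and death is mRS 6. This stands: exclusion from the whole test is one possible reading and not a stated rule. It does not close the gap. On the generous reading the dead count through mRS while MoCA, EQ-5D and, if used, SIS remain survivor-only.

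A reader might also infer that the cognitive component cannot be formed for most patients. The documents do not support that. The number of centres repeating Trails B is not given, the telephone MoCA is scheduled centrally for everyone at 12 months, and section 28 acknowledges that some tests lose items by telephone. T-MoCA is probably what is meant; the fault is that it is not named.

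It is also fair that survivors-only scale results are legitimate if labelled, that physical disability is itself a target of the trial so more weight on function is not necessarily a distortion, and that this is an additional analysis in a trial whose primary endpoint is recruitment and retention. Excess mortality would still show in Tables 2 and 3, in the composite, in the fatal columns of Tables 6a–c and 7a–c, and in the survival analysis of Protocol section 9.2. These points limit the importance of the issue. They do not remove the conflicting definitions.

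**Conclusion.** The point holds in three parts.

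- The global outcome has two definitions, differing in the Stroke Impact Scale and in whether imaging-detected stroke is stated to count, and no rule chooses between them.
- The 12-month cognitive instrument is not identified.
- Death has no score on six 12-month scales. About 7–8 of 363 patients would therefore leave those Table 3 rows under section 20, and may be lost from the matching global components.

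The reading that all 12-month rows lose the deaths goes too far: mRS and both ordinal cognition scales keep them. So does the reading that the global test leaves out death altogether, because that is not stated.

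The expected size is moderate. In the simulation the choice of list changed the verdict in a minority of runs, and the handling of death mattered mainly when mortality differed between arms. Those rates rest on the assumed correlations, effect, mortality and equal weights. The issue should be corrected, but it does not touch the primary endpoint.

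**What to change.** Before the soft lock:

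1. State one component list and one stroke definition, identically in section 29 and the Table 3 footnote, with the component weights. Which list to keep is the sponsor's decision; a short reason should be recorded.
2. Name T-MoCA as the 12-month cognitive component, in the global outcome and in the MoCA row of Table 3.
3. Code every component in one direction, since higher is worse on mRS but better on MoCA and EQ-5D.
4. Prespecify a worst-rank score for death on every global component and on every 12-month scale, consistent with mRS 6 and the ordinal cognition scales. For EQ-5D, check that the value chosen is no better than the worst living state in the value set used. Give survivors-only results as a labelled sensitivity analysis.
5. State how a patient with some components missing enters the test, including how stroke is scored when the repeat MRI was not done.

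The cost is SAP wording and a few lines of code, with no new data. The downside is that means including a score for death are slightly harder to interpret clinically, which the survivors-only results offset.

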We will categorise cognition into 7- and 4-level ordinal scales based on DSM-V²² categorisation (Table E).²³ We will calculate scores for cognitive domains using sub-scores of MoCA (or TICS if missing) although we recognise that these global cognitive assessments have some test items that map to a more than one domain, e.g. the

clock drawing test in the MoCA includes aspects of attention, executive function and visual-perceptual function.

- Learning and memory: orientation in place (from MoCA), delayed recall of five word (MoCA), and recall and delayed recall of ten words (TICS)
- Language: using comprehension, semantic and recent memory (from MoCA; similar elements in TICS-M)
- Perceptual-motor function: Cube copy and clock drawing from MoCA
- Executive function: Trail making tests A & B, verbal fluency test (VFT-phonemic)-F (from MoCA); verbal fluency test (VFT-semantic)-animals; clock drawing test (from MoCA); digits forward (from MoCA); digits backward (from MoCA)
- Complex attention: using serial sevens subtraction (MoCA), letter tapping (MoCA)
- Social cognition is not classically assessed in cognitive screening tools and there are no agreed generic short form assessments for social cognition. Aspects of social cognition will be assessed through informant data and NPI-Q although these are not part of the core outcome set.

Table E. Categorisation of cognition based on DSM V with operationalisation (adapted summary from ²³).

	Seven-level categorisation and operationalisation	Four-level categorisation and operationalisation
Normal cognition	No evidence of cognitive impairment (T-MoCA:20-22 AND TICS-m: 25-39)	No evidence of cognitive impairment (T-MoCA:20-22 AND TICS-m: 25-39)
Minor Neurocognitive disorder (mild cognitive impairment)	Single domain Scores are reduced by > 1 point in only one cognitive domain of T-MoCA	Evidence of cognitive impairment (T-MoCA: 15-19 OR TICS-m: 17-24) AND
	Multi-domain Scores are reduced by > 1 point in more than one cognitive domain of T-MoCA	No evidence of functional impairment (mRS <2 OR no change in mRS if pre-stroke mRS >1)
Major neurocognitive disorder	Mild cognitive impairments (T-MoCA 15-19 OR TICS-m 17-23) AND Mild dysfunction (mRS <3)	Persisting cognitive impairment (T-MoCA score <19 OR TICS-m<24 on more than one follow-up) AND Functional impairment (mRS ≥2 or IQCODE >3.6 at final follow-up)

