	Moderate cognitive impairments (T-MoCA 10-14 OR TICS-m 12-16) AND Moderate dysfunction (mRS 3 or 4)	OR Any clinical diagnosis of dementia made independent of study, e.g. by memory clinic, in primary care, recording of dementia on death certification, prescription of cholinesterase inhibitor or memantine
	Severe cognitive impairments (T-MoCA <10 OR TICS-m <12) AND Severe dysfunction	

	In a care-home OR mRS 4,5	
Death	Death (mRS 6)	Death (mRS 6)

30 Harms

These are presented as serious adverse events in Tables 6a-c and 7a-c.

31 Statistical software

Statistical Analysis System (SAS) version 9.4, SAS Institute Incorporation, Cary, North Carolina.

SECTION 7. ADDITIONAL INFORMATION

Confounding covariates

The primary outcome is recruitment, and this will be tabulated; as such, there are no confounding covariates.

The possible primary outcome in any following trial will likely be a composite comprising MACE, dementia or mild cognitive impairment, non-vascular death and new MRI signs and these event rates will be assessed in the current trial. The components are likely to be correlated. Example confounding variables are given and these are categorised by whether these were 'measured', as per routine practice, or 'unmeasured'; the latter will lead to residual confounding.

Composite outcome

Measured variables: Age, highest educational attainment, main occupation, socioeconomic status, stroke severity, function at randomisation, cognitive ability at randomisation, diabetes mellitus, hypertension, smoking, carotid disease, blood pressure, prescribed medications, time from stroke to randomisation, presence of a relevant infarct and SVD lesion severity on brain imaging.

Unmeasured: Examples are social isolation, vision, hearing, cardiac function (atrial fibrillation and heart failure are documented) and post-stroke complications.

Governance

LACI-2 is funded by the British Heart Foundation (CS/15/5/31475) and approved by the East Midlands – Nottingham 2 Research Ethics Committee (Ref: 17/EM/0077). The Sponsor is the ACCORD office, University of Edinburgh and NHS Lothian. NHS Research and Development/ Innovation approval is given at each participating site. The study is adopted by the National Institute for Health Research (NIHR) Clinical Research Network in England and the Stroke Research Network in Scotland.

Minimising bias

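### SAP Table E's rules for the 7- and 4-level cognition scales overlap and leave gaps, with no order of precedence, so some fully observed participants get two levels or none

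*SAP*

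**What the plan says.** Table E in SAP section 29 gives two columns of rules, and the SAP presents it as an adapted summary of a cited cohort protocol.

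- Normal, both scales: "No evidence of cognitive impairment (T-MoCA:20-22 AND TICS-m: 25-39".
- 7-level Minor depends only on T-MoCA domain scores. The multi-domain row is "Scores are reduced by > 1 point in more than one cognitive domain of T-MoCA"; the single-domain row is the same for exactly one domain. Neither has a total-score or functional limit.
- 7-level Major-mild: "Mild cognitive impairments (T-MoCA 15-19 OR TICS-m 17-23) AND Mild dysfunction (mRS <3".
- 7-level Major-moderate: "Moderate cognitive impairments (T-MoCA 10-14 OR TICS-m 12-16) AND Moderate dysfunction (mRS 3 or 4".
- 7-level Major-severe: T-MoCA below 10 or TICS-m below 12, together with care-home residence or mRS 4 or 5.
- 4-level Minor: "Evidence of cognitive impairment (T-MoCA: 15-19 OR TICS-m: 17-24) AND" "No evidence of functional impairment (mRS <2 OR no change in mRS if pre-stroke mRS >1".
- 4-level Major: "Persisting cognitive impairment (T-MoCA score <19 OR TICS-m<24 on more than one follow-up) AND" "Functional impairment (mRS ≥2 or IQCODE >3.6 at final follow-up". An independent clinical diagnosis of dementia also qualifies.

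Table C schedules TICS and t-MOCA at months 6 and 12 only, so impairment at more than one follow-up means impairment at both. The full MOCA is done at baseline. Table 3 lists both scales as 12-month outcomes, marks ordinal logistic regression against the 7-level scale, and calls the 4-level Major category Dementia. Figure 3 gives subgroup interactions for the 7-level scale; Figures 6 and 7 plot the two distributions.

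**The concern.** An ordinal outcome needs a rule that sends every observed state to exactly one level. Table E does not do this, and the SAP states neither an order of precedence nor a residual category. It also does not say what happens to a participant who fits no row. Section 20 restricts regressions to complete data, while section 28 says the available data will be used as fully as possible, and section 28 concerns missing data rather than complete but unclassifiable data.

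The programmer would therefore have to choose the missing rules. Section 13a plans tabulation and analysis at a soft lock, so choices left until then would be made with outcome data in hand. One participant could also appear as Minor in Figure 7 and as Major in Figure 6.

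**Working it through.** The documents give no numerical target here, so the check applies each printed rule to specific states. Scores are T-MoCA / TICS-m / mRS at 12 months. Persistent means the same scores at month 6.

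**Cut-offs side by side**

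- TICS-m 24 lies in 4-level Minor (17-24), but outside 7-level Major-mild (17-23) and 4-level Major (<24).
- T-MoCA 19 lies in 7-level Major-mild (15-19), but outside 4-level Major (<19).
- mRS 4 lies in both Major-moderate (3 or 4) and Major-severe (4, 5).

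**States with two levels**

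| State | Rules met |
|---|---|
| 12/10/4 | Major-moderate (T-MoCA 10-14, mRS 4) and Major-severe (TICS-m <12, mRS 4) |
| 17/28/1, one T-MoCA domain down by more than 1 | 7-level Minor single-domain and Major-mild (T-MoCA 15-19, mRS <3) |
| 17/20/0, persistent, IQCODE >3.6 | 4-level Minor (T-MoCA 15-19, mRS <2) and 4-level Major (T-MoCA <19 twice, IQCODE >3.6) |

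**States with no level**

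| State | Why |
|---|---|
| 12/14/1, IQCODE ≤3.6, no diagnosis | Four levels: both scores fall below the Minor bands, and Major fails on function |
| 19/24/2, persistent, pre-stroke mRS 0, IQCODE ≤3.6, no diagnosis | Four levels: Minor fails on function; Major fails because 19 is not <19 and 24 is not <24. It meets 7-level Major-mild |
| 21/24 at any mRS 0-5 | Seven levels: TICS-m 24 is too low for Normal and too high for Major-mild. With the printed T-MoCA maximum of 22, only 22 − 21 = 1 point is lost, so no T-MoCA domain can be down by more than 1 |

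The last row is conditional. Table E scores domains from T-MoCA, but the text above it also draws on TICS word recall, Trails A and B and animal fluency. If those items count, a domain could be down by more than 1 and the participant would be Minor.

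**Comparison of the scales.** Take 18/20/0 with IQCODE ≤3.6 and no diagnosis. On four levels it is Minor only. On seven levels it meets Major-mild, and also Minor if a domain is down by more than 1. Under worst-level precedence it would be Major-mild, so the scales would differ. The same holds for every state with T-MoCA 15-19 or TICS-m 17-23, mRS 0-1, IQCODE ≤3.6 and no diagnosis: the 7-level row admits mRS 0-2, while the 4-level column treats mRS 0-1 as no functional impairment.

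**What precedence alone would leave open.** Worst-level precedence removes overlaps but fills no gap. It also leaves 12/14/1 with at most 7-level Minor while 17/20/1 meets Major-mild, so lower scores on both tests at the same mRS give the better level. For Major severity, take both tests in the same band: 3 bands × 6 mRS values = 18 pairs. Outside a care home, a Major level is printed for 3 + 2 + 2 = 7. For care-home residents the severe band is covered at all six mRS values, giving 3 + 2 + 6 = 11.

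**Leftovers on four levels.** With worst-level precedence and cut-offs of ≤19 and ≤24, enumeration over T-MoCA 0-22, TICS-m 0-39, mRS 0-5, pre-stroke mRS 0-2, IQCODE, diagnosis and persistence leaves two kinds of state unassigned: functional impairment with cognitive impairment at one follow-up only, and scores outside the Minor bands, not Normal, without functional impairment.

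**Side effect of those cut-offs.** Persistent 19/24/1 with IQCODE >3.6 is Minor only as printed and becomes Major. Persistent 21/24/3 (no diagnosis) has no level as printed and becomes Major.

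**The case against.** The strongest reply has four parts.

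- Table E is a summary of a cited protocol that may hold a complete algorithm. That is possible, but the SAP neither reproduces those rules nor tells the programmer to apply them.
- Worst level wins is the natural convention. It may be, but it is not written down, and it does not fill gaps.
- The two scales serve different purposes: one uses persistence and IQCODE, the other grades severity, and nothing in the SAP requires one to collapse into the other. This stands. A difference between the scales is not in itself an error; the plan should say that it can happen.
- These are additional analyses, and Table 3 also reports MoCA, TICS-m, cognitive impairment and clinical dementia separately. This stands too and limits the importance of the point.

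A reader might infer more than the documents support. The share of score combinations with two levels or none is not a share of participants, because the documents do not give the joint distribution of scores. Nor can one infer that the composite outcome is compromised: the SAP does not say that its cognitive-impairment component comes from Table E. The 21/24 gap is not unconditional, because it depends on how domains are scored.

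**Conclusion.** The point holds. Followed exactly, Table E gives some participants with complete data two levels and others none, and the SAP has no rule to settle either case. The two-level and 4-level gap examples need only the printed cut-offs and the stated values. The 7-level gap at 21/24 assumes domains scored from T-MoCA alone with a maximum of 22. The disagreement between scales at 18/20/0 is certain if no domain is down by more than 1, and otherwise follows from worst-level precedence.

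Reach is limited to the Table 3 cognition-scale rows and Figures 3, 6 and 7. The primary feasibility endpoint is untouched. The number of participants affected is unknown. This should be fixed because the repair is cheap and the affected results are otherwise not determined by the plan.

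**What to change.** Before any tabulation, including the soft lock, and blind to allocation, replace Table E with a complete derivation (the cited source's full algorithm would serve if it meets step 5):

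1. State that the worst qualifying level applies, with Death first.
2. Put mRS 4 in one Major level, and make the T-MoCA and TICS-m cut-offs consistent between rows and columns. If ≤19 and ≤24 are chosen, as the complement of the Normal row, say openly that this widens the level Table 3 calls Dementia compared with the printed <19 and <24, and show the printed cut-offs as a sensitivity analysis.
3. Assign each leftover state to a stated level: impairment at one follow-up only, scores below the Minor bands without functional impairment, the uncovered pairs of score band and mRS, and a missing IQCODE or 6-month test. Show the alternative assignment as a sensitivity analysis.
4. State which items make up each domain and the reference against which a loss of more than 1 point is measured.
5. Check by enumeration that every state receives exactly one level.

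Making the 4-level scale an exact collapse of the 7-level one is optional. If it is not done, state that the two can differ for the same participant.

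The cost is SAP wording and derivation code, with no new data. Category counts may no longer match the source cohort's. Worst-level precedence also removes the Minor placement of a persistently impaired participant whose pre-stroke mRS of 2 is unchanged, unless that exemption is written into the Major row. Placing single-visit impairment remains a judgement, which is why the sensitivity analysis is needed.
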